4.10.2 Ki-67 Labelling Index

Ki-67 labelling index will be assessed and expressed as the average percentage of tumour cells with counted positive nuclei, following the International Ki-67 in Breast Cancer Working Group Recommendations. Ki-67 labelling index will be scored by increments of 1% and can range from 0 – 100. When the number of tumour cells per section for a counted biopsy is less than 100 tumour cells, then the Ki-67 labelling index is not reported and NE will be stated.

The secondary pharmacodynamic biomarker variables of change from baseline in Ki-67 labelling index after 5 to 7 days of AZD9833 treatment for Stage 1 and Stage 2; and after 12 to 15 days of AZD9833 treatment for Stage 3 will be listed and summarised based on the PD analysis set (see Section 4.5).

It is expected that the distribution of the Ki-67 labelling index data will not be normally distributed (Robertson et al 2013, Robertson et al 2020b), hence Ki-67 labelling index data will be naturally log-transformed before being analysed. Ki-67 will be analysed similarly to ER and PgR, using a parametric ANCOVA on natural log transformed data. Values equal to zero on the original scale will be set to one (1), and one will be added to the corresponding baseline/biopsy day labelling index value before natural log transformation. Log transformed baseline score will be included as a covariate, and day of biopsy and treatment group included as fixed effects. The estimated treatment effect together with 80% CIs for all treatment durations (5 to 7 consecutive days of AZD9833 treatment for stage 1 and stage 2, and 12 to 15 consecutive days of AZD9833 treatment for stage 3), as per the model fitted will be back transformed to the original scale for reporting. For listings, original values will be reported.

Sensitivity analyses for Ki-67 labelling index

If necessary, sensitivity analysis will be conducted on a subset of the PD analysis set by excluding:

- Any patients who are considered to be HER2 positive by central assessment.
- Any patients with a Ki-67 labelling index < 5% from their pre-treatment biopsy.
- Any patients with an ER H-score < 10 on their pre-treatment biopsy.
- Any patients with an ER H-score < 10 on their pre-treatment biopsy or any patients with a Ki-67 labelling index < 5% from their pre-treatment biopsy.

If considered necessary, further cuts and sensitivity analyses may be performed.

If, following transformation of the data, an ANCOVA model is still not appropriate, a non-parametric approach may be considered.

4.11 Safety Evaluation

All safety summaries will be based upon the Safety Analysis Set and presented for all patients by Stage 1 and Stage 2 combined, Stage 3 alone and Stages 1, 2 and 3 combined by actual treatment group.

4.11.1 Extent of Exposure

Extent of exposure for AZD9833 will be defined in terms of the number of days the treatment is received.

Exposure (i.e., duration of treatment) will be defined as follows:

$$\text{Total exposure} = \min(\text{last day of dosing, date of death, date of withdrawal}) - \text{first dose date} + 1.$$

$$\text{Actual exposure} = \text{total exposure of study treatment} - \text{total duration of dose interruptions}$$

where total exposure will be calculated as above, and a dose interruption is defined as any length of time (number of days) where the patient has not taken any of the planned daily dose. This should be taken from the patient diary cards.

RDI is defined as the percentage of the actual dose delivered relative to the intended dose through to treatment discontinuation. Relative dose intensity will be calculated as follows:

$$\text{RDI}(\%) = \frac{d}{D} \times 100,$$

where

- d the actual cumulative dose delivered (which will be taken from the patient diary card)
- D the intended cumulative dose (duration of intended dose will be calculated from Day 1 to the planned biopsy day. D is the total dose that would have been delivered if there were no modification to dose or schedule).

If a patient permanently discontinues study treatment, then the date of last administration of study medication recorded on eCRF will be used to program the RDI. If a patient permanently discontinues study treatment during a treatment interruption, then the date of last administration of study medication recorded on the eCRF will be used to program the RDI.

Summaries

The exposure data will be summarised and listed for the safety analysis set including all data from the diary card (see [Section 4.5](#)).

For AZD9833 treatment groups, actual treatment duration, total treatment duration, RDI, and the number and percentage of patients that received at least 5 consecutive days of dosing for Stage 1 and Stage 2; and at least 12 consecutive days of treatment for Stage 3 will be summarised. In addition, the number and percentage of patients who received the planned starting dose of AZD9833, with no interruption, with dose interruption or discontinuation and with both dose interruption and discontinuation will be presented. Reason for dose interruption and dose discontinuation will also be summarised.

4.11.2 Adverse Events

AEs and SAEs will be collected throughout the study from date of informed consent until the end of the safety follow-up period (28 days after last dose of study treatment). The latest version of MedDRA will be used to code the AEs. AEs will be graded according to the National Cancer Institute of Common Terminology Criteria for AEs (CTCAE) version 5.0.

Events will be defined as treatment-emergent AEs, and reported in the summary tables if they onset or worsen (by investigator report of a change in CTCAE grade), during the treatment period as defined in the CSP or during the 28-day safety follow-up period. Any events in this period that occur after a patient has received further therapy for cancer (following discontinuation of study treatment) will be flagged in the data listings.

During the evaluation of the AE data prior to database lock, an AZ medically qualified expert will review the list of AEs that were not reported as SAEs and AEs leading to discontinuation of study treatment. Based on the expert's judgment, significant AEs of particular clinical importance may, after consultation with the Global Patient Safety Physician, be considered other significant AEs (OAEs) and reported as such in the CSR. A similar review of laboratory/vital signs/ECG data will be performed for identification of OAEs.

Examples of these could be marked haematological and other laboratory abnormalities, and certain events that lead to intervention (other than those already classified as serious), dose reduction or significant additional treatment.

Some clinical concepts (including some selected individual preferred terms and higher-level terms) are considered to be "AEs of special interest" (AESIs). AESIs represent pre-specified risks that are considered to be of importance to a clinical development program. These AESIs, if applicable, will be identified as a list of categories provided by the patient safety team.

Reviews will take place prior to database lock to determine whether any AE should be classified as AESIs. The review will identify which higher-level terms, and which preferred terms should contribute to each AESI.

In general, all AE summary tables include only TEAEs. AEs occurring prior to dosing or starting more than 28 days after discontinuation of study drug will be flagged in listings and will not be included in any summaries.

All reported AEs will be listed along with the actual treatment received at the time of onset, date of onset, date of resolution (if AE is resolved), investigator's assessment of CTCAE grade, relationship to study treatment, action taken and outcome. Frequencies and percentages of patients reporting each preferred term will be presented (i.e., multiple events per patient will not be accounted for, except for event level summaries).

Summaries of adverse events (the number and percentage of patients by treatment) by MedDRA System Organ Class (SOC) and Preferred Term (PT) will include but are not limited to:

- All AEs
- All AEs possibly related to study treatment
- AEs of CTCAE grade 3 or higher
- AEs of CTCAE grade 3 or higher, possibly related to treatment
- AEs with outcome of death
- All SAEs
- All SAEs possibly related to study treatment
- AEs leading to discontinuation of treatment

- AEs leading to discontinuation of treatment, possibly related to treatment
- SAEs leading to discontinuation of treatment
- SAEs leading to discontinuation of treatment, possibly related to treatment
- Other significant AEs (if applicable)
- AESIs (if applicable)

An overall summary of the number and percentage of patients in each of the above categories will be presented, as well as an overall summary of number of events in each of the above categories. In addition, a truncated AE table of most common AEs, showing all events that occur in at least 5% of patients overall will be summarised by PT, by decreasing frequency.

Additionally, an event level summary will be presented for all AEs by PT.

Summaries of the number and percentage of patients with AEs will also be produced by maximum reported CTCAE grades, SOC and PT.

All AESI PTs, if applicable, searched for in this study will be presented. Summaries of AESIs will be presented by maximum reported CTCAE grade, by AE outcome, including time of resolution (on-treatment, follow-up or post-treatment), whether treatment was received (yes/no) and action taken.

In addition, AEs with outcome death, SAEs, AEs leading to discontinuation of treatment and OAEs will be listed separately.

Covid-19 AEs will also be collected and reported by MedDRA System Organ Class.

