4.3 General Variables

4.3.1 Study Day Definitions

Study day 1 is defined as the date of first dose of study treatment.

For visits (or events) that occur on or after first dose of study treatment:

Study day = Date of visit [event] – Date of first dose of study treatment + 1.

For visits (events) that occur prior to first dose:

Study day = Date of visit [event] – Date of first dose of study treatment.

There is no study day 0 defined for this study.

For listings (such as AEs) that include the derivation “Days since last dose”, days will be defined as:

Days since last dose = Event date – Date of last dose.

Where “Date of last dose” is defined as the date of dosing immediately preceding the event occurrence. Events that occur on the same day as the last dose of study treatment will therefore be described as occurring zero days from last dose of study treatment.

All visit-based summaries will use eCRF visits as shown in [Table 2](#). There won’t be any visit windowing defined for on-treatment visits for this study. If there is more than one value per patient within an analysis visit then the closest value to the intended visit date will be summarised, or the earlier, in the event the values are equidistant from the protocol intended visit date. The 28th day safety follow-up is from the last day of dose administration of AZD9833. Any adverse event and concomitant medication data collected after the last dose of study treatment until 28 ± 3 days will be included in the relevant summaries. For summaries of the minimum or maximum observed value whilst on treatment, all data recorded at any time point (including unscheduled visits) will have the potential to be summarised. All results will be presented by treatment group and by visit with descriptive statistics appropriate to the nature of the variables.

Table 2: Analysis visit mapping

For Stage 1 and Stage 2

eCRF visit	Protocol visit	Protocol visit window	Analysis visit
Visit 1	Screening ^a	Day -21 to Day 1 (pre-dose)	Baseline
Visit 2	First day of dosing ^a	Day 1 (pre-dose)	
Visit 3	Biopsy Day	Day 5, Day 6 or Day 7	Biopsy day
Visit 4	Surgery Day	≥ Day 11	Surgery day
Visit 5	28 Day follow-up after the last dose of the study treatment	≥Biopsy Day +25 days to ≤Biopsy Day +31 days	Follow-up

^a The last non missing value obtained prior to the first dose/administration of study medication will be considered as baseline.

For Stage 3

eCRF visit	Protocol visit	Protocol visit window	Analysis visit

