4.3.2.2 Imputation of Adverse Event and Concomitant Medication End Date

Missing day: impute with the last day of the month, unless month and year are the same as month and year of last dose of study treatment, then impute with the last treatment date in that month.

Missing day and month: impute with 31st of December unless the year is the same as the year of last dose of the study treatment, then impute with the last treatment date of that year.

Completely missing: assume the event is still ongoing and do not impute any date.

Generally, the imputation of dates is to decide if an observation is treatment emergent for AEs or concomitant for medications. Flags will be retained in the database indicating where any

programmatic imputation has been applied, and in such cases, durations and study days will not be calculated.

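### SAP Section 4.11.2 counts a pre-dose AE that worsens on treatment as treatment-emergent, but a later sentence bars pre-dose AEs from all summaries without exception

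*SAP*

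**What the plan says.** Section 4.11.2 of the SAP sets out four things that bear on this point.

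- Collection: "AEs and SAEs will be collected throughout the study from date of informed consent" to the end of the safety follow-up. Table 2 in Section 4.3.1 lets screening start at Day -21.
- Definition: events are treatment-emergent and "reported in the summary tables if they onset or worsen (by investigator report of a change in CTCAE grade), during the treatment period" or the 28-day safety follow-up.
- General table rule: "In general, all AE summary tables include only TEAEs".
- Exclusion, directly after the general rule: "AEs occurring prior to dosing or starting more than 28 days after discontinuation of study drug will be flagged in listings and will not" enter the tables. Its scope is every summary, since such AEs are to be "flagged in listings and will not be included in any summaries".

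Two other places touch on how the flag would be derived. Section 4.3.2.2 says "Generally, the imputation of dates is to decide if an observation is treatment emergent for AEs or concomitant for medications"; the imputation rules cover start and end dates only. On listings, Section 4.11.2 says "All reported AEs will be listed along with the actual treatment received at the time of onset, date of onset, date of resolution", together with grade, relationship, action taken and outcome. Neither place mentions a date of grade change.

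Section 4.3.1 separately includes AE data collected after the last dose, up to 28 ± 3 days, in the relevant summaries.

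**The concern.** The definition includes worsening so that an event already present at first dose is counted when it becomes more severe on drug. The exclusion sentence, taken at its word, removes the pre-dose events to which that part of the definition applies. A programmer who builds the exclusion from the AE start date would satisfy that sentence and contradict the definition.

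AEs and SAEs are secondary endpoints (Section 2.2), and Section 4.11 summarises safety by actual treatment group. The tables at risk are those where worsening matters most: grade 3 or higher, maximum CTCAE grade, possibly related events, and events leading to discontinuation. If the start-date reading is used, the error runs one way. It can remove on-treatment worsening from a table but cannot add any.

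**Working it through.** The SAP states no figure on this point, so the main check is to apply the definition and the exclusion to each type of AE record.

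| AE record | Definition (starts or worsens in the window) | Exclusion sentence (plain wording) | Agree? |
|---|---|---|---|
| Onset before dosing, no worsening | out | out | yes |
| Onset before dosing, worsens on treatment or in follow-up | **in** | **out** | **no** |
| Onset on treatment or within 28 days after | in | not excluded | yes |
| Onset more than 28 days after discontinuation | out | out | yes |

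The two rules part company in the second row only. As an illustration, take nausea that starts at grade 1 on Day -5 and reaches grade 3 on Day 4, held as one record. It is tabulated under the definition and left out under the exclusion.

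The last row agrees within Section 4.11.2 but not fully with Section 4.3.1. An AE that starts 29 to 31 days after the last dose falls inside 28 ± 3 days and outside the 28-day cut-off.

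**What one patient is worth.** Evaluable numbers per group come from Sections 3.1 to 3.3 and 4.13. The share is 1/n.

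- 75 mg and 150 mg, Stages 1 and 2: n = 12 + 24 = 36; 1/36 = 2.8 points.
- 75 mg and 150 mg, Stage 3: n = 24; 1/24 = 4.2 points.
- 75 mg and 150 mg, all stages: n = 36 + 24 = 60; 1/60 = 1.7 points.
- 300 mg: n = 12 evaluable; 1/12 = 8.3 points. Using the 14 per group that Section 4.13 recruits in Stage 1 to allow for 15% drop-out (12/0.85 = 14.1), and assuming the same allowance here, 1/14 = 7.1 points.

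The safety set takes in every dosed patient, so true denominators may be somewhat larger and these shares somewhat smaller. In a patient-level row, a lost event changes the count only if that patient has no other event in the same row.

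**The case against.** The best defence is that the exclusion sentence was meant only as the complement of the definition. It directly follows the statement that tables in general hold treatment-emergent events, and it speaks of AEs occurring before dosing but starting after the window. An event that worsens on Day 4 is still occurring on treatment, so one can argue that it was never excluded. This reading is plausible and may well be what was intended. It is not written down, however: the exclusion covers any summary, carries no exception, and nothing elsewhere in the SAP reconciles the two sentences.

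The second defence is that worsening may be recorded as a new AE with its own on-treatment start date. Even a strict start-date filter would then keep it. Recording conventions commonly sit in the protocol or eCRF instructions, which are not shown, so this may be settled there. It would remove the loss of events but leave the SAP wording in conflict.

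The third is that nothing is hidden. All reported AEs are listed with grade, and SAEs, deaths and AEs leading to discontinuation have their own listings. This stands, and it limits the consequence to the tables.

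A reader might also infer that a fall in grade, say from 2 to 1, counts as treatment-emergent because the definition mentions a change in grade. The text does not support that. The governing verb is worsen, and the parenthesis says only how worsening is identified.

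**Conclusion.** The conflict in wording is real and confined to one record type: AEs with onset before first dose that worsen during treatment or the 28-day follow-up. Such events are lost from the tables only if two conditions both hold: the exclusion is applied by onset date, and worsening is not captured as a separate AE record. The SAP fixes neither.

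A reader might go further and infer that AE rates by dose will be biased downward. The document does not support this as a certainty. The downward direction follows only under those two conditions, and the SAP gives no basis for estimating how many events would be affected.

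The weight of one patient runs from about 1.7 to 4.2 points at 75 mg and 150 mg, depending on which stages are pooled. A figure of 7 to 8 points applies only to groups of 12 to 14, meaning the 300 mg group or the Stage 1 review, and should not be carried over to the pooled tables. This is a modest but genuine inconsistency in a secondary safety endpoint, and it should be corrected.

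**What to change.** Rewrite the exclusion so that it mirrors the definition, for example: *AEs with onset before first dose that do not worsen in CTCAE grade on or after first dose, and AEs starting after the end of the AE reporting window, will be flagged in listings and not summarised.* Define that window once, so that the 28-day cut-off in Section 4.11.2 and the 28 ± 3 days in Section 4.3.1 agree.

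State also which record or date drives the treatment-emergent flag when an event worsens: a new AE record, or a dated grade change on the existing one. Writing increase in place of change in the definition is optional tidying.

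The cost is a few sentences in the SAP and a matching check of one derived flag. No new analyses are needed, and no new data provided that worsening is already captured in one of those two ways.

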4.11.3 Deaths

A summary of deaths will be provided with number and percentage of patients, categorised as:

- Related to disease under investigation only
- AE outcome = death only
- Both related to disease under investigation and with AE outcome = death
- Other deaths.

A corresponding listing will also be produced.

4.11.4 Clinical Laboratory Evaluation

All laboratory results collected will be listed.

Summaries for safety laboratory will only include the parameters specified in [Table 5](#).

All values will be classified as low (below range), normal (within range), or high (above range) based on local laboratory reference ranges. Results will be converted to standard units and graded with CTCAE version 5.0.

Table 5: Laboratory safety variables

Haematology (whole blood)	Clinical chemistry (serum or plasma)
B-Haemoglobin	S/P-Creatinine
B-Leukocyte count	S/P-Bilirubin, total (TBL)
B-Haematocrit	S/P-Conjugated bilirubin
B-Red blood cell count	S/P-Unconjugated bilirubin
B-Leukocyte differential count (absolute count)	S/P-Alkaline phosphatase (ALP)
Neutrophils	S/P-Aspartate transaminase (AST)
Lymphocytes	S/P-Alanine transaminase (ALT)
Monocytes	S/P-Creatine kinase (CK)

Basophils	S/P-Albumin
Eosinophils	S/P-Calcium, total
B-Platelet count	S/P-Potassium
Coagulation Parameters	S/P-Sodium
Prothrombin time (PTT)	S/P-Glucose
Activated partial thromboplastin time	S/P-Magnesium
International normalised ratio	S/P-Phosphate
Urinalysis (dipstick)	S/P-Urea or Urea nitrogen
U-Glucose	S/P-Protein, total
U-Protein	S/P-Troponin I
U-Blood	S/P-Troponin T
	S/P-NT-proBNP

If the same parameter is found as measured in serum and in plasma, then the summaries will not distinguish between them (e.g., values from plasma albumin and serum albumin will be summarised under albumin). If the same parameter is found as measured in serum and in plasma within the same patient, which would be a rare case, then the change from baseline will only be calculated for those post-baseline values using the same source, i.e., only within plasma or serum. If one patient has multiple toxicity grades, because they are derived separately from serum and plasma then the maximum value of the two will be considered.

Corrected calcium will be calculated as:

Corrected calcium (mg/dL) = $0.8 \times (\text{normal albumin} - \text{patients albumin}) + \text{total serum calcium}$
or

Corrected calcium (mmol/L) = $0.02 \times (\text{normal albumin} - \text{patients albumin}) + \text{total serum calcium}$
depending on the unit used.

For all continuous laboratory assessments, absolute value, change from baseline and percentage change from baseline will be summarised using descriptive statistics at each scheduled assessment time by actual treatment group.

For clinical chemistry and haematology, shift tables will present movements from baseline to worst value on-treatment (defined from start of treatment to biopsy day) according to reference range classification. CTCAE grade changes from baseline to on-treatment will also be provided. Corresponding shift tables (“Negative”, “Trace”, “Positive”, “0”, “+”, “++”, “+++”) will be produced for urinalysis. In addition, the number of patients with ≥ 2 CTCAE grade changes and CTCAE grade changes to 3 or 4 will be summarised by actual treatment group for clinical chemistry and haematology parameters.

Plots for both maximum post-baseline alanine transaminase (ALT) and aspartate transaminase (AST) versus the maximum post-baseline total bilirubin (expressed as multiples of their upper limit of normal [ULN] reference range) will be produced with reference lines at 3 x ULN for ALT and AST and 2 x ULN for total bilirubin. Box plots of absolute values and change from baseline values for all haematology and clinical chemistry parameters will also be presented.

Liver biochemistry test results over time for patients who show elevated ALT or AST (≥ 3 x ULN) and elevated bilirubin (≥ 2 x ULN) (elevated results do not need to be present at the same visit) or ALT or AST of ≥ 5 x ULN, will be tabulated and plotted.

